3.2. Study Endpoints

3.2.1. Primary Endpoint

The primary endpoint is the area under the time-corrected endogenous creatinine clearance curve from Day 1 to Day 7 (AUC_{1-7}) calculated as the average of the standardized endogenous creatinine clearance values over the 7 days.

3.2.2. Key Secondary Endpoint

The key secondary endpoint is renal replacement therapy (RRT) incidence during the period Day 1 (after first treatment) to Day 28, inclusive.

3.2.3. Other Secondary Endpoints

Renal endpoints include the following:

- Volume of urine (daily from Day 1 to Day 7, inclusive, and on subsequent visit days if reliable 6 hour urine collection is possible) normalized per hour.
- Serum creatinine and blood urea nitrogen (BUN)/urea (daily from Day 1 to Day 7, inclusive, and on subsequent visit days)
- BUN/Urea clearance daily from Day 1 to Day 7 inclusive, and on subsequent visit days if reliable urine collection is possible.
- Peak value of serum creatinine and peak values of BUN/urea (during the period Day 1 to Day 7, inclusive)
- RRT-free days. An RRT-free day is defined as a day on which a patient did not receive any form of RRT.
- Total number of days on RRT (during the period Day 1 to Day 28, inclusive). A day on RRT is defined as a day on which a patient received any form of RRT (including RRT with interruptions) for any period of time on that day.
- Reasons for initiation of RRT (during the period Day 1 to Day 28, inclusive)

- Kidney function at Day 14, 21 and 28 as assessed by measured creatinine clearance if available, otherwise as assessed by estimated glomerular filtration rate (eGFR) (estimated by the CKD-EPI formula based on serum creatinine)
- Kidney function at Day 60 and Day 90 as assessed by eGFR (estimated by the CKD-EPI formula based on serum creatinine).
- Sustained loss of kidney function at Day 60 and Day 90, defined by eGFR < 60 mL/min (with eGFR estimated by the CKD-EPI formula based on serum creatinine).
- Incidence of dialysis dependency at Day 60 and Day 90.

Endpoints for organs other than renal function include the following:

- Liver enzymes (aspartate aminotransferase (AST), alanine aminotransferase (ALT), gamma-glutamyl transpeptidase (GGT), lactate dehydrogenase (LDH), bilirubin but excluding alkaline phosphatase (AP)).
- Lung function as assessed by fraction $\text{PaO}_2/\text{FiO}_2$ (P/F ratio) Carrico index, positive end expiratory pressure (PEEP), and tidal volume in mechanically ventilated patients.
- Mechanical ventilator-free days (from Day 1 to Day 28, inclusive). A ventilator-free day is defined as a day on which a patient was not on ventilator (invasive or non-invasive mechanical ventilation).
- Time from start of first administration of study drug to being off- mechanical ventilator (from Day 1 to Day 28, inclusive) for those patients who are on mechanical ventilator at the start of this period.
- Shock-free days (during the period Day 1 to Day 28, inclusive). A patient is considered to be shock free if he or she is not on vasopressors or inotropic agents (including but not limited to noradrenaline, adrenaline, dobutamine, dopamine, vasopressin, or enoximone).
- Time from start of first administration of treatment to being shock free (from Day 1 to Day 28, inclusive) for those patients who are not shock free at the start of this period.
- System Organ Failure Assessment (SOFA) scores during ICU/Intermediate care stay.
- Number of dysfunctional organs as assessed by SOFA scores (from Baseline to Day 28, inclusive).
- Deaths during the 90-day study period (by recording date).

Biomarker endpoints include the following:

- Kidney function markers.
- Tubular injury biomarkers.
- Biomarkers for systemic inflammation.
- Pharmacokinetics of recAP in all 3 active treatment groups during Part 1 of the study.
- In addition to recAP PK concentration measurements, baseline (pre-dose) AP will be measured by activity (central laboratory).

3.2.4. Other Endpoints

Additional endpoints include the following:

- Composite endpoints – patients that meet, or do not meet, at least 1 of the following criteria:
 - Received RRT or died (prior to Day 28 [inclusive]).
 - $\text{eGFR} < 60$ mL/min (at Day 60, estimated by the CKD-EPI formula), or dialysis dependency, or died (prior to Day 60).

- eGFR < 60 mL/min (at Day 90, estimated by the CKD-EPI formula), or dialysis dependency, hospitalized for a new episode of AKI (at Day 90), or died (prior to Day 90).
- Serology as assessed by immunoglobulin G (IgG), immunoglobulin E (IgE), and total immunoglobulin.
- Safety parameters including (Serious) adverse events ((S)AEs), laboratory assessments (clinical chemistry, hematology, and urinalysis parameters not considered in the efficacy analysis), vital signs, and electrocardiogram (ECG) data.
- Quality of life, assessed by the EuroQol-5D (EQ-5D) questionnaire at baseline, ICU/Intermediate care discharge, and Day 90.
- Time from start of first administration of treatment to discharge from ICU/Intermediate care where discharge is defined as the time when the decision was made to transfer the patient (as opposed to the time of actual transfer).
- Total time in ICU/Intermediate care from the start of first administration of study drug (during the period Day 1 to Day 28 inclusive and during the period Day 1 to Day 90, inclusive) using the time of actual transfer
- Time from start of first administration of treatment to discharge from hospital where discharge is defined as the time when the decision was made to transfer the patient (as opposed to the time of actual transfer).
- Total time in hospital from the start of first administration of study drug (during the period Day 1 to Day 28, inclusive and during the period Day 1 to Day 90, inclusive) using the time of actual transfer.

3.3. Treatments

Study drug will be administered by 1-hour IV infusion as soon as possible on Day 1, and 24 ± 1 hours later on Days 2 and 3, by trained staff in the ICU/Intermediate care. A total of 50 mL will be infused at a constant rate of 50 mL/hour. At the start of each drug administration, the exact volume of recAP or placebo to be administered to each patient will be determined according to the patient's weight at screening. The volume of the placebo and the volume of the active doses of recAP are identical. The preferred route for study drug administration will be through a central line; if this is not possible, a peripheral line will be acceptable. Study drug will be administered separately from any concomitant drugs using a dedicated lumen of the catheter.

3.4. Dose Adjustment/Modifications

Infusion of the study drug may be temporarily interrupted or permanently discontinued for a variety of reasons, including an adverse event or equipment malfunction. Therefore, it is possible that the total study drug dose and volume planned for a patient may differ from the total dose and volume administered and any such patients will be identified on the study drug infusion listing (see [Section 7.2](#)).

4. General Statistical Considerations

Combined analysis of primary endpoint

As described in [Section 8.1.1](#), the primary efficacy endpoint for this study is analyzed at both the interim analysis (based on all patients recruited in Part 1 up to that point) and at the end of the study (using all patients recruited after conclusion of Part 1, i.e. during Part 2). Patients recruited whilst the interim analysis is performed will be handled as follows:

- Those recruited to the optimal dose or placebo will form part of the Part 2 populations.
- Those recruited to the other doses will not be included in any efficacy analysis (except one sensitivity analysis on the primary endpoint), but their safety data will be analyzed.

The results from each analysis are then combined using an inverse normal method. This combined analysis of patients from Parts 1 and 2 rests on the assumption that patients recruited in each part of the study will belong to the same overall patient population. To check this assumption, data related to the baseline characteristics and demographics (for the selected optimal dose and placebo groups) will be repeated for Part 1 and Part 2. If any notable differences are observed, then the combined analysis will need to be interpreted with caution and further exploratory analysis will need to be conducted to investigate the possible causes.

The assumption of a consistent treatment effect across Parts 1 and 2 will be investigated by repeating the primary and key secondary efficacy analyses (for the optimal recAP dose and placebo treatment groups) for Part 1 and Part 2. Again, any notable differences will lead to the associated combined analysis being interpreted with caution and further exploratory analyses conducted to investigate the possible causes.

Combined analysis of secondary and ‘other’ endpoints

Efficacy endpoints will be summarized for all four treatment groups excluding patients recruited whilst the interim analysis is performed to treatment arms not selected for Part 2. Any analyses of the other efficacy endpoints will compare the optimal recAP dose and placebo treatment groups only. All safety data will be summarized for all four treatment

groups including patients recruited at any point in the study. Similarly, all data listings will include patients recruited at any point in the study.

See also [Section 4.3](#) for definitions of the analysis sets used in the study, which also state which patients (i.e. recruited during Part 1, or recruited during Part 2) are included in each analysis set.

Display of data

Continuous variables will be summarized using descriptive statistics, including but not limited to the mean, standard deviation, median, lower quartile, upper quartile, minimum value, and maximum value. For the summary statistics of all numerical variables minimum and maximum will be displayed to the same level of precision as reported, unless otherwise specified. Mean, median, lower quartile and upper quartile will be displayed to one level of precision greater than the data collected. Standard deviation / standard error will be displayed to two levels of precision greater than the data collected. P-values will be rounded to three decimal places. If a p-value is less than 0.001 it will be reported as “<0.001.” If a p-value is greater than 0.999 it will be reported as “>0.999”.

Categorical variables will be summarized using frequency counts and percentages. When count data are presented, the percentage will be suppressed if the count is zero in order to draw attention to the non-zero counts. The denominator for all percentages will be the number of patients in that treatment within the analysis set of interest, unless otherwise specified. All percentages will be presented to one decimal place. Categorical summaries will display all categories available on the electronic case report form (eCRF). A row denoted “Missing” will be included in count tabulations only when information is missing for a categorical variable.

All data summaries will be provided by treatment arm.

All data collected across the 4 treatment groups throughout the study will be listed in data listings. Data will be displayed in all listings sorted by treatment group, patient ID and other variables as appropriate. Patients will be identified in the listings by the patient identification number concatenated with the investigator number.

In the case that there are no data available for a table, listing or figure, e.g. no serious adverse events (SAE) within the trial, an output should be created but state “There are no data to display for this [table/listing/figure].”

Definition of baseline

Unless otherwise specified, baseline will be defined as the last non-missing evaluation prior to the first infusion of study treatment. For the efficacy analyses which are based on

the ITT analysis set, any subjects who were not dosed will have their baseline defined as the last non-missing evaluation.

Study Time

Study day is defined as:

Assessment date - first infusion date of study treatment + 1.

Assessments will be performed during a total of 12 visits, at the following intervals: daily from Day 1 to Day 6; Day 7 + 1 day; weekly on Day 14 ± 2 days, Day 21 ± 3 days, and Day 28 ± 3 days; and follow-up assessments will be completed on Day 60 ± 5 days and Day 90 ± 10 days.

Method of assigning patients to received treatment group

Actual treatment received for a patient will be calculated as the average dose received over the three treatment days. The average dose received will be determined according to the treatment kit dispensed to the patient (per the materials/kit schedule) and the volume of infusion received as recorded on the treatment administration page of the eCRF.

For the safety and per protocol (PP) analyses, patients are analyzed according to their received treatment group. Using the average dose received over the three treatment days, each patient will be assigned to a received treatment group based on the dose windows defined in [Table 4-1](#).

Table 4-1 Actual Treatment Dose Assignment

Average dose received	Received treatment group assignment
>0.0 – 0.62 mg/kg	recAP 0.4 mg/kg [250 U/kg]
>0.62 – 1.23 mg/kg	recAP 0.8 mg/kg [500 U/kg]
>1.23 mg/kg	recAP 1.6 mg/kg [1000 U/kg]

Please note that any patients who do not receive any dose of study drug will be excluded from the safety and PP analyses, and therefore do not need to be considered in the [Table 4-1](#). Dose windows were constructed in line with the weight ranges and corresponding pre-calculating volumes displayed in [Table 15-3](#). See [Section 15.3](#) for full justification of these windows.

Statistical Analysis

All statistical tests will be two-sided and performed using a 5% significance level, displaying 95% two-sided confidence intervals (CIs), unless specifically stated otherwise. As the primary efficacy endpoint is analyzed at the interim analysis and at the end of the study, multiplicity will be addressed by using a combination test to combine the results (see [Section 8.1.1](#)). A hierarchical method will be employed to address any multiplicity arising from the analysis of the key secondary endpoint. In other words, the formal analysis of this endpoint will be performed only if a statistically significant result is obtained from the combination test analysis of the primary endpoint. All analyses performed on the other secondary endpoints are for exploratory purposes only; therefore, no further multiplicity adjustment is required.

All analyses will be undertaken using SAS[®] Version 9.2 (SAS Institute, Inc, Cary, North Carolina) or later.

Weight

Body weight (in kg or lb) will be measured or estimated at screening. Weight will be displayed in kg and derived from lb as:

$$Weight[kg] = \frac{Weight[lb]}{2.2046}$$

Temperature

Temperature (in °C or °F) will be measured from Day 1 – Day 28. Temperature will be displayed in °C and derived from °F as:

$$Temperature[°C] = \frac{Temperature[°F] - 32}{1.8}$$

Laboratory Data

For laboratory data that are recorded as values of '<x' and '>x' where x is any numeric value, the numeric part after the '>' and '<' (i.e. x) will be used for summarizing and in graphical presentations. In addition the numeric part will be used in the derivation of the quartile-based subgroup definitions.

In the tables where serum creatinine or CRP data are presented, if a subject has missing baseline central laboratory measured serum creatinine or CRP values, but has available baseline local laboratory measured values then the local laboratory values will be used to

reduce the number of missing baseline values in the analyses. This does not apply to the calculation of endogenous creatinine clearance. The following conversion rates will be used to convert the local lab measured value to mg/dL (if source unit is different):

Table 4-2 Serum Creatinine and CRP Laboratory Conversions

Parameter	Source Unit	Standard unit	Conversion rate
Serum creatinine	mg/L	mg/dL	0.1
	umol/L	mg/dL	0.0113122
CRP	mg/L	mg/dL	0.1
	nmol/L	mg/dL	0.0105

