## **5.4 Management of Clinical Supplies**

### **5.4.1 Study Drug Packaging and Storage**

Recombinant human AP active 8 mg/mL and matching placebo will be prepared in randomized treatment packs comprising 3 daily doses, each of 4 vials (in any combination of recAP drug product and placebo) and shipped by PPD to the clinical site. Each pack will contain a (randomized) dosage for 1 patient and will contain a sufficient quantity for dispensing during the 3-day double-blind treatment period.

The labeling of recAP and matching placebo will be in accordance with applicable local requirements in the countries where this study is conducted.

Recombinant human AP must be stored in a secure area protected from light and kept at a controlled temperature of 2°C to 8°C.

Full details of study drug packaging, storage, and shipment will be provided in the pharmacy manual.

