4.3.4. Safety

The Safety Set includes all patients who were randomly assigned and received a dose of study drug. All safety analyses will be based on the Safety Set, with patients analyzed according to the treatment they received.

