7.2.1. Extent of Exposure

The number and percentages of patients that received any dose on Day 1, Day 2 and Day 3 will be summarized by treatment group. The number and percentages of patients will also be presented by total number of doses received (1 dose, 2 doses, 3 doses) by treatment group. All summaries will be performed using the Safety Set. The number and percentage of patients who discontinued the study prior to receiving treatment on Day 1, Day 2 and Day 3 will also be included.

Study Drug Infusion information will be presented in the form of a listing for the Safety Set, including: was patient dosed (Yes, No); infusion start time; infusion end time; route of

administration (central line, peripheral line); volume of all 4 vials drawn into the 50 mL syringe (yes, no); volume from the 4 vials discarded from the syringe based on patients weight (mL); saline added to the 50 mL syringe (mL), was total volume of 50 mL syringe administered (yes, no), and, if no, reason why total volume was not administered; and total volume of study drug administered (mL).

8. Efficacy Analysis

A hierarchical method will be employed to address any multiplicity arising from the analysis of the key secondary endpoint. In other words, the formal analysis of this endpoint will be performed only if a statistically significant result is obtained from the combination test analysis of the primary endpoint. All analyses performed on the other secondary endpoints are for exploratory purposes only; therefore, no further multiplicity adjustment is required. The results of this hierarchical method will be presented indicating where statistically significant results are obtained.

To provide an overall summary of the efficacy analyses, a table will be produced containing the results and magnitude of difference between the optimal recAP dose and placebo treatment groups for certain key endpoints. This table will be based on the ITT Combined Set.

Supportive analysis will be undertaken on a selection of endpoints (AUC_{1-7} and RRT incidence from Day 1 to Day 28, inclusive) including specific group categories as factors to assess the consistency of treatment effects.

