15.3. Weight Ranges and Pre-calculated Corresponding Volumes

Table 15-3 Weight Ranges and Pre-calculated Corresponding Volumes

Body weight (kg)	Body weight (lb)	Volume drawn from 4 vials (mL)	Volume discarded from syringe (mL)	IMP retained in syringe (mL)	Saline added to reconstitute (mL)	Total volume in syringe (mL)
35 < 40	77 < 88	20	12	8	42	50
40 < 45	88 < 99	20	11	9	41	50
45 < 50	99 < 110	20	10	10	40	50
50 < 55	110 < 121	20	9	11	39	50
55 < 60	121 < 132	20	8	12	38	50
60 < 65	132 < 143	20	7	13	37	50
65 < 70	143 < 154	20	6	14	36	50
70 < 75	154 < 165	20	5	15	35	50
75 < 80	165 < 176	20	4	16	34	50
80 < 85	176 < 187	20	3	17	33	50
85 < 90	187 < 198	20	2	18	32	50
90 < 95	198 < 209	20	1	19	31	50
95 - 115	209 < 253	20	0	20	30	50

Abbreviation: I

IMP = investigational medical product.

In line with [Table 15-3](#), the volume of investigational product (mL) administered to each patient is defined for a range of body weights – hence, the dose (mg/kg) can vary slightly dependent on where a patient lies within a weight range, even if the infusion is prepared correctly. The investigation product has a concentration of 8 mg/mL, thus the exact dose is calculated as

$$\frac{5 \times \text{IMP retained in syringe (mL)} \times \text{Treatment group}}{\text{Weight (kg)}}$$

where Treatment group = 0.4, 0.8, and 1.6 respectively for the recAP groups. The minimum doses for a correctly prepared infusion (corresponding to the maximum weight within each range in [Table 15-3](#)) are 0.4 mg/kg, 0.8 mg/kg and 1.6 mg/kg respectively for each of the recAP treatment groups. The maximum doses (corresponding to a patient with body weight 35 kg) are 0.457 mg/kg, 0.914 mg/kg and 1.829 mg/kg respectively.

Therefore, the dose windows in Section 4 used to assign patients to received treatment group based on average dose are based on the average midpoints between the minimum and maximum possible doses of each weight group for each treatment group (0.62 mg/kg for the split between the 0.4 mg/kg and 0.8 mg/kg groups; and 1.23 mg/kg as the cutoff between the 0.8 mg/kg and 1.6 mg/kg groups).

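### Received-treatment group is set from dose averaged over three days with no rule for missed or stopped infusions, so early stoppers on 0.8 and 1.6 mg/kg can be tabulated under a lower dose

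*SAP*

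**What the plan says.** SAP Section 4, under the method of assigning patients to received treatment group, states: "Actual treatment received for a patient will be calculated as the average dose received over the three treatment days". The dose comes from the kit dispensed and the infused volume recorded in the eCRF. Table 4-1 then assigns the group: up to 0.62 mg/kg is the 0.4 group, above 0.62 and up to 1.23 is the 0.8 group, and above 1.23 is the 1.6 group. The scope is explicit: "For the safety and per protocol (PP) analyses, patients are analyzed according to their received treatment group". SAP 4.3.4 agrees: "All safety analyses will be based on the Safety Set, with patients analyzed according to the treatment they received".

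The only exception, in the note to Table 4-1, is that "any patients who do not receive any dose of study drug will be excluded from the safety and PP analyses".

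Incomplete courses are expected. SAP 3.4 foresees interruption and permanent discontinuation, including for adverse events, so that "it is possible that the total study drug dose and volume planned for a patient may differ from the total dose and volume administered"; such patients are identified in a listing. SAP 7.2.1 tabulates the "total number of doses received (1 dose, 2 doses, 3 doses) by treatment group".

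SAP 15.3 justifies the cut-offs from correctly prepared infusions only. It says that the minimum doses, at the top of each weight range, "are 0.4 mg/kg, 0.8 mg/kg and 1.6 mg/kg respectively for each of the recAP treatment groups".

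**The concern.** The SAP does not say whether a missed day counts as zero or is left out of the divisor. Two programmers could build different safety tables from the same paragraph.

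The literal reading is a divisor of three. Under it, the shift runs one way and depends on outcome. A 1.6 mg/kg patient withdrawn for an adverse event after one or two infusions could not appear in the 1.6 column of the table of TEAEs leading to treatment discontinuation (SAP 9.1.5). The tables of TEAEs, SAEs, causes of death and laboratory data (SAP 9.1.1, 9.1.4, 9.1.6, 9.2) are open to the same shift. Placebo keeps its early stoppers; the lower active columns gain them from above. In a dose-finding study this can hide a dose–toxicity gradient.

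The number-of-doses table would also be distorted. With full-volume infusions, the 1.6 column could contain only three-dose patients and the 0.8 column no one-dose patients.

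The interim and DMC safety outputs in SAP 11 are Safety Set tables, and dose choice depends on the DMC seeing no safety issue with the dose (SAP 3.1).

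**Working it through.** **Inputs.** Dose per infusion = 5 × mL retained × group / weight (SAP 15.3). Volumes run from 8 mL at 35–<40 kg to 20 mL at 95–115 kg (Table 15-3). Cut-offs are 0.62 and 1.23 mg/kg (Table 4-1). Maximum weight is 115 kg (Protocol 5.2).

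**Step 1: reproduce the SAP's figures.** At 35 kg, 5 × 8 × group / 35 gives 0.457, 0.914 and 1.829 mg/kg, the stated maxima. For the cut-offs, take the midpoint between the lower group's maximum and the higher group's minimum in each weight band, then average over the 12 bands below 95 kg. This gives 0.617 and 1.2348, in line with the stated 0.62 and 1.23.

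**Step 2: range of a correctly prepared infusion.** The lowest dose is at 115 kg: 5 × 20 × group / 115 = 0.348, 0.696 and 1.391. The full ranges are 0.348–0.457, 0.696–0.914 and 1.391–1.829, all inside the right windows.

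**Step 3: divisor of three, full-volume infusions.** Average = infusions given × dose / 3, over 35–115 kg:

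| Arm (mg/kg) | 1 infusion | 2 infusions | 3 infusions |
|---|---|---|---|
| 0.4 | 0.116–0.152, stays | 0.232–0.305, stays | 0.348–0.457, stays |
| 0.8 | 0.232–0.305, to 0.4 | 0.464–0.610, to 0.4 | 0.696–0.914, stays |
| 1.6 | 0.464–0.610, to 0.4 | 0.928–1.219, to 0.8 | 1.391–1.829, stays |

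Even the most favourable weight, 35 kg, does not escape: 1.829 / 3 = 0.610 ≤ 0.62, and 2 × 1.829 / 3 = 1.219 ≤ 1.23. The move therefore affects 100% of 0.8 and 1.6 mg/kg patients with one or two full infusions, and none with three.

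**Step 4: divisor equal to infusions given.** Full infusions stay in place. A single infusion moves the patient down when its volume share is at or below f = cut-off / full dose:

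- 1.6 arm: 1.23/1.829 = 67.3% (35 kg) to 1.23/1.391 = 88.4% (115 kg).
- 0.8 arm: 0.62/0.914 = 67.8% to 0.62/0.696 = 89.1%.

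With one full and one stopped infusion, the second must exceed 2f − 1 to keep the patient in place: 34.5–76.8% (1.6 arm) and 35.6–78.3% (0.8 arm).

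**Step 5: the minimum doses in SAP 15.3.** The stated minima of 0.4, 0.8 and 1.6 do not match the 95–115 kg row, which gives 0.348, 0.696 and 1.391 at 115 kg. From the stated minima, the tolerated volume shortfall would be 1 − 1.23/1.6 = 23.1% and 1 − 0.62/0.8 = 22.5%. At 115 kg it is 1 − 1.23/1.391 = 11.6% and 1 − 0.62/0.696 = 10.9%.

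**The case against.** The strongest reply is that the harm depends on an unstated reading. SAP 15.3 derives the windows from single-infusion doses, which suggests an average over infusions given; on that reading no full-volume patient moves. This stands as a limit: the misclassification in Step 3 is conditional. It does not remove the gap, because Section 4 refers to the three days twice and never states the other divisor.

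A second reply is that analysing patients by what they received is the stated convention, so a patient who got less drug belongs in a lower window. Nothing in the documents requires classification by kit. But an infusion stopped for an adverse event was given at its own dose level, and moving the event to another column misstates where it arose. Reduced exposure already has its own table and listing.

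Third, Protocol 5.2 gives 95–115 kg patients the dose for 100 kg, and 20 mL at 100 kg is exactly 0.4, 0.8 or 1.6 mg/kg. That explains the minima. The sentence in SAP 15.3 still refers to the maximum weight in each range, so it conflicts with its own table, although no correctly prepared infusion is misclassified.

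Finally, the reach is limited, and this stands. No safety test is planned. The Day 28 and Day 90 mortality comparisons use the ITT Combined Set. The infusion listing identifies these patients, although a listing does not correct a summary table.

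**Conclusion.** The concern holds. The rule for received treatment is incomplete. Followed literally, it reassigns every 0.8 and 1.6 mg/kg patient with one or two full infusions to a lower dose. Under the alternative divisor, partial infusions can still move patients.

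How many patients this affects cannot be derived, because the documents give no rate of incomplete treatment. For scale only, under a divisor of three: if 0.8 or 1.6 mg/kg is selected, 30 + 85 = 115 patients are planned on it, so each 1% missing an infusion is 1.15 patients. The other of those two arms adds 30 from Part 1 plus any interim recruits. If 0.4 mg/kg is selected, only the dropped 0.8 and 1.6 arms (30 each, plus interim recruits) can move.

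The effect falls on descriptive safety tables. ITT efficacy is unaffected. A per-protocol effect is confined to patients with at least five of seven clearance values and no significant deviation. Protocol 7.5 gives a wrong drug volume as an example of such a deviation; whether a missed or stopped infusion counts is left to a separate rules document. This should be fixed before the safety tables are produced.

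**What to change.** - Assign the received group by the dose level of the kit dispensed, and state that missed, interrupted or partial infusions do not change it. Protocol 5.4.1 describes "randomized treatment packs comprising 3 daily doses, each of 4 vials", with one pack per patient, so this is a single value unless there is a dispensing error.
- Use the 0.62 and 1.23 windows only to flag preparation errors, applied to the prepared dose per infusion (5 × mL retained × kit level / weight). By Step 2, no correctly prepared infusion would be flagged.
- Pre-specify how a flagged patient, or one given kits of different levels, is classified.
- Show incomplete exposure through the planned number-of-doses table and infusion listing.
- Reconcile the minimum doses stated in SAP 15.3 with the 95–115 kg row.
- State which rule produced the interim and DMC safety tables; SAP 8.1.4 indicates that the interim has already been run.

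Defining the divisor as infusions given would be a smaller change, but it leaves the partial-infusion problem in Step 4.

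The cost is one SAP paragraph, one derivation change and the correction to SAP 15.3. No new data are needed.
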